The primary endpoint is the pharyngeal cure rate – that is, the proportion of subjects who return for TOC who clear their infections as evidenced by a negative culture 4-7 (+/-1) days after treatment. Persons who test negative for NG at their enrollment visit (i.e. infection cleared between initial clinical screening test and enrollment) will be excluded from analysis. Treatment failure will be defined as a positive culture 4-7 (+/-1) days after treatment. The cure rate will be calculated as the number of cured subjects divided by the total number of subjects who received treatment and returned for follow-up testing in a modified an intention to treat (mITT) analysis. We will also calculate the 95% CI for this proportion.

We will conduct an interim analysis after we have primary outcome results for 25 subjects. If the cure rate is $\leq 44\%$ (99% CI 17% – 74%; i.e. 12 persons of 25 persons with a positive culture on treatment date fail treatment), we will stop the study. We will also monitor for renal toxicity at the interim analysis. We plan to obtain pre-treatment and post-treatment Creatinine. Increases $>40\%$ will be considered significant. If more than 20% of the study population has a $>40\%$ increase in serum Creatinine, we will halt the study. We chose 20% because if 20% of subjects experience renal toxicity it is unlikely to be due to chance (95% CI 7 – 40%). For our second objective, we will compare the MIC of cures to treatment failures using a stratified approach (Table 2), and we will correlate this data with individual peak gentamicin level in order to estimate the ideal pharmacodynamic (PD) criterion (Obj. 2). For persons who fail treatment we will also compare the pre- and post-treatment genatmicin MIC to estimate whether single dose gentamicin therapy can “induce” resistance (Obj. 3) as an exploratory analysis. We will consider an increase in the MIC by two doubling-dilutions (i.e. from MIC of 2 to 8 $\mu\text{g/mL}$, or 8 to 32 $\mu\text{g/mL}$) to represent induced resistance, and we will calculate the

proportion of isolates among those that fail treatment that demonstrate induced resistance following receipt of gentamicin. Lastly, we will report the number and proportion of subjects who report side effects.

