The Medical Monitor, [name], will review study conduct including efficacy and renal toxicity and AEs in aggregate on at a single interim analysis after 25 subjects, and at the end of the study. The Medical Monitor will review serious adverse events (SAEs), hearing loss, and serious drug allergies in real-time. Study data are provided to the Medical Monitor prior to the interim and final analysis. Data reports are prepared by the PI, [name].

MONITORING REPORT

The Medical Monitor, [name], will provide a written report to the study team with recommendations for study modification, study continuation/discontinuation as relevant. The study team is responsible for forwarding the report to the IRB.

COLLECTION AND REPORTING OF SAEs AND AEs

For this study, the following standard AE definitions are used:

Adverse event: Any unfavorable and unintended sign (including an abnormal laboratory finding), symptom or disease temporally associated with the use of a medical treatment or procedure, regardless of whether it is considered related to the medical treatment or procedure.

Serious Adverse Event: Any AE that results in any of the following outcomes:

- Death
- Life-threatening
- Event requiring inpatient hospitalization or prolongation of existing hospitalization
- Persistent or significant disability/incapacity

AEs are graded according to the following scale:

Mild: An experience that is transient, & requires no special treatment or intervention. The experience does not generally interfere with usual daily activities. This includes transient laboratory test alterations.

Moderate: An experience that is alleviated with simple therapeutic treatments. The experience impacts usual daily activities. Includes laboratory test alterations indicating injury, but without long-term risk.

Severe: An experience that requires therapeutic intervention. The experience interrupts usual daily activities. If hospitalization (or prolongation of hospitalization) is required for treatment it becomes an SAE.

The study uses the following AE attribution:

Not related: The AE is clearly not related to the study procedures (i.e., another cause of the event is most plausible and/or a clinically plausible temporal sequence is inconsistent with the onset of the event).

Possibly related: An event that follows a reasonable temporal sequence from the initiation of study procedures, but that could readily have been produced by a number of other factors.

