Related: The AE is clearly related to the study procedures.

AEs are identified at the TOC visit using the symptom screen, and with Creatinine monitoring.

SAEs and specific procedure-associated AEs are reported to the Medical Monitor within 24 hours. In addition, all AEs are reported according to the University of Washington AE reporting guidelines.

MANAGEMENT OF RISKS TO SUBJECTS

Expected AEs

Expected AEs associated with gentamicin include:

- Pain at injection site
- Bruising at injection site

AE Management

- Warm compresses as needed
- Tylenol as needed

DATA ANALYSIS PLANS

The Medical Monitor will conduct interim analyses after we have primary outcome results for 10 and 25 subjects. (Enrollment will pause until analyses can be conducted). Stopping rules include the primary end point (i.e. pharyngeal cure rate), and adverse events. If after 10 and 25 subjects, the cure rate is $\leq 44\%$ (99% CI 17% – 74%; i.e. 11 persons of 25 persons with a positive culture on treatment date fail treatment), we will stop the study. We chose these numbers using the O'Brien-Fleming method of alpha spending for multiple analyses, assuming an alpha of 0.003 for the first analysis and an alpha of 0.049 for the final analysis. Using the 99% CI obtained with 11/25 treatment failures, the upper bound is less than 75%. (Our hypothesis is that gentamicin alone will be 80% effective for pharyngeal gonorrhea, with the goal to use it in combination with a second agent). Alternatively, if at interim analysis more than 20% of subjects (99% CI 20% - 46%) have a greater than 40% increase in their creatinine from baseline, we will halt the study.

Data Analysis

The proposed study aims to evaluate the efficacy of a single intramuscular (IM) dose of 360 mg of gentamicin in the treatment of pharyngeal gonorrhea. Secondary objectives include evaluating the renal safety and tolerability of 360mg of gentamicin, *documenting peak serum gentamicin levels by subject weight*, and estimating the ideal pharmacodynamic criterion using a combination of peak gentamicin concentration levels compared to MIC and treatment outcomes. *In exploratory analyses*, we will attempt to determine whether gentamicin-monotherapy induces antimicrobial resistance among treatment failures. The specific aims are:

- 1) Determine the proportion of persons whose pharyngeal gonococcal infections are cured with a single dose of 360mg gentamicin intramuscularly alone.

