As a means to preserve funding and ensure safety, we will conduct interim analyses after we have primary outcome results for 10 and 25 subjects. (Enrollment will pause until analyses can be conducted). Stopping rules include the primary end point (i.e. pharyngeal cure rate), and adverse events. If after 25 subjects, the cure rate is $\leq 44\%$ (99% CI 17% – 74%; i.e. 11 persons of 25 persons with a positive culture on treatment date fail treatment), we will stop the study. We chose these numbers using the O'Brien-Fleming method of alpha spending for multiple analyses, assuming an alpha of 0.003 for the first analysis and an alpha of 0.049 for the final analysis. Using the 99% CI obtained with 11/25 treatment failures, the upper bound is less than 75%. Alternatively, if at interim analysis 32% or more of subjects (99% CI 9.4% - 63%) have a greater than 40% increase in their creatinine from baseline, we will halt the study.

Appendices

- A. Clinician Information and Referral Script
- B. Study Info Card
- C. Appointment Reminder Card
- D. Screening Eligibility Form
- E. Enrollment visit data entry form
- F. TOC visit data entry form

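### The plan schedules one interim look in some sections and two in others, and only one section applies the 44% cure stop at 10 subjects, where the support given for 44% at 25 does not carry over

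*Combined protocol and SAP*

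**What the plan says.** Four places describe the interim looks.

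- **Synopsis, Statistical Analysis Plan:** "We will conduct an interim analysis after we have primary outcome results for 25 subjects". No look at 10 is mentioned. Renal toxicity is monitored at that interim.
- **Data Safety and Monitoring Plan, Monitoring Procedures:** the Medical Monitor reviews efficacy, renal toxicity and adverse events in aggregate "at a single interim analysis after 25 subjects" and again at study end. Under Monitoring Report, the Monitor then issues "recommendations for study modification, study continuation/discontinuation as relevant".
- **Same plan, Data Analysis Plans:** "The Medical Monitor will conduct interim analyses after we have primary outcome results for 10 and 25 subjects". The cure stop reads "If after 10 and 25 subjects, the cure rate is" 44% or lower.
- **Data Analysis, Analyses (last paragraph):** "As a means to preserve funding and ensure safety, we will conduct interim analyses after we have primary outcome results for 10 and 25 subjects". It adds "Stopping rules include the primary end point (i.e. pharyngeal cure rate), and adverse events", but the cure threshold reads "If after 25 subjects, the cure rate is" 44% or lower. None is given for 10.

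The last two places support 44% with an interval of 17% to 74%, labelled 99%, and an upper bound under 75%, all tied to 25 subjects. They list one alpha for the first analysis (0.003) and one for the final (0.049). The creatinine halt is triggered at more than 20% of subjects in the synopsis and in Data Analysis Plans, and at 32% or more in Data Analysis.

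**The concern.** A stopping rule should give one answer for one set of data, and here it does not. If 4 or fewer of the first 10 evaluable subjects are cured, Data Analysis Plans stops the study. Data Analysis holds a look but states no cure threshold for it, although it names the primary end point as a stopping criterion. The synopsis and Monitoring Procedures schedule no formal look at that point. The Medical Monitor, who must recommend continuing or not, has two schedules within one monitoring plan.

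The 44% limit is also moved to 10 subjects without the calculation that supports it at 25. At stake are whether, and how early, a poorly performing treatment is stopped. The creatinine halt is exposed to the same schedule conflict.

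**Working it through.** **1. The plan's own interval.** The exact (Clopper-Pearson) limits for x cured of n are the beta quantiles B(α/2; x, n−x+1) and B(1−α/2; x+1, n−x). For 11 cured of 25 (44%):

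- α = 0.003 (99.7%): 17.1% to 73.8%, which matches the printed 17% to 74%.
- α = 0.01 (99%): 19.7% to 70.5%.

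The printed interval is thus numerically a 99.7% interval, consistent with the stated alpha of 0.003. At that level 11 is the largest count with an upper bound under 75%; 12 cured gives 77.0%.

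**2. The same argument at 10.** The largest count at or below 44% is 4 of 10 (40%).

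| Cured of 10 | Exact 99% upper | Exact 99.7% upper |
|---|---|---|
| 4 | 80.9% | 84.8% |
| 3 | 73.5% | 78.2% |
| 2 | 64.8% | 70.2% |

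For 4 of 10 the Wilson upper bound is 75.2% (99%, a marginal miss) or 78.5% (99.7%). Only a 95% exact interval gets under 75% (73.8%), and the plan does not use 95% for this rule.

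**3. How often the conflict arises.** P(X ≤ 4), X ~ Binomial(10, p). The 80% is the plan's hypothesis; lower rates are assumed. The Executive Summary allows that pharyngeal efficacy may fall short of genital efficacy.

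**4. What it changes.** Compare a cure stop at 10 and 25 with a stop at 25 only, where the study stops at k or fewer cured of 25. The final outcome differs with probability D = Σ (i = 0 to 4) P(X₁₀ = i) · P(X₁₅ > k − i). Timing alone differs with probability P(X₁₀ ≤ 4) − D.

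Example, p = 0.60, k = 11: D = 0.00010×0.0905 + 0.00157×0.2173 + 0.01062×0.4032 + 0.04247×0.6098 + 0.11148×0.7869 = 0.118. Timing only = 0.166 − 0.118 = 0.048.

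The text supports three readings of k: 11 (11 cured), 13 (12 failures, synopsis) and 14 (11 failures, the two later sections).

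| True cure | P(≤4/10) | Outcome differs, k = 11 / 13 / 14 | Timing only, k = 11 / 13 / 14 |
|---|---|---|---|
| 80% | 0.6% | 0.6 / 0.6 / 0.5% | about 0.1% or less |
| 60% | 16.6% | 11.8 / 5.5 / 2.8% | 4.8 / 11.1 / 13.8% |
| 50% | 37.7% | 14.5 / 3.9 / 1.4% | 23.2 / 33.8 / 36.3% |
| 40% | 63.3% | 7.8 / 1.1 / 0.3% | 55.5 / 62.2 / 63.0% |

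**5. The count at 25.** Failures of 11 and 12 leave 14/25 = 56% and 13/25 = 52% cured, not 44%. Their exact 99.7% upper bounds are 83.0% and 80.1%. The 44%, the 17% to 74% and the bound below 75% together fit 11 cured.

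**6. Creatinine halt.** As an illustration, 3 of 10 subjects (30%) over the creatinine limit would halt the study under Data Analysis Plans and not under Data Analysis. Under Monitoring Procedures they would have no scheduled aggregate review at that point.

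**The case against.** Each section can be carried out on its own, and at the hypothesised 80% cure the cure-rule conflict arises in only 0.6% of studies. Both points stand. The synopsis merely omits a look at 10; only Monitoring Procedures excludes one expressly. The investigators also review all data in real time, so early failures would not go unseen. What is missing is a scheduled formal decision.

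It is also fair that the plan reports the 75% bound as a property of the result at 25, not as a test for every look. The finding is therefore that the stated support does not extend to 10, not that the plan breaks a rule it set for 10. The Wilson miss at 99% is only 0.2 points.

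Four stronger readings are tempting and are not supported:

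- **The extra look inflates a false efficacy claim.** The rule stops only for low cure, and the primary analysis is a proportion with a 95% interval. The absence of an alpha for a look at 10 is a gap in description.
- **Only the cure rule is affected.** Monitoring Procedures also places renal review at the single look, and the creatinine thresholds differ.
- **Only timing is affected.** That holds at 50% cure or below. At 60% with k = 11, the outcome differs more often (11.8%) than timing alone (4.8%).
- **Exactly 15 more people would be treated.** The gap is 25 − 10 = 15 evaluable subjects. Treated people who are negative at enrolment or do not return are not counted, so 15 is a minimum.

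**Conclusion.** The contradiction is in the current text and should be fixed. Sections disagree on whether there are one or two interim looks, two of them instruct the same Medical Monitor differently, and only one applies the cure stop at 10. The support given for 44% does not carry over to 4 of 10 by the exact interval at 99% or 99.7%, and narrowly fails by Wilson at 99%.

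The practical effect is negligible if cure is near 80% and substantial if it is low: a 37.7% chance of conflicting instructions at an assumed 50%. At 50% or below the conflict mainly moves the stop between 10 and 25 evaluable subjects. At 60%, with the 25-subject rule read as 11 or fewer cured, it more often changes whether the study stops at all. These figures assume independent outcomes with a constant cure rate, and that each rule is followed as written.

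**What to change.** 1. Make the synopsis, Monitoring Procedures, Data Analysis Plans and Data Analysis agree on the number of looks and on which of them the cure rule applies to.
2. If the cure rule is kept at 10, derive its count from the plan's own upper-bound argument (below 75%) at a named interval method and confidence level, and state the same rule in Data Analysis Plans and Data Analysis. With the exact interval the count would be 3 or fewer at 99%, or 2 or fewer at 99.7%. If the rule is not kept at 10, delete the reference to 10 from the cure rule in Data Analysis Plans.
3. Reconcile the creatinine halt across the same sections, both its threshold and the looks it applies to. This review proposes neither.
4. In the same edit, settle whether the count at 25 means subjects cured or subjects failing, and make it agree with 44% and the printed interval.

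The change is to protocol wording only. The possible cost is a lower chance of stopping at 10 when cure is low. At a true 50% that chance is 37.7% with 4 or fewer of 10, 17.2% with 3 or fewer, 5.5% with 2 or fewer, and zero if the cure rule at 10 is dropped.

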The proposed study aims to evaluate the efficacy of a single intramuscular (IM) dose of gentamicin in the treatment of pharyngeal gonorrhea. Secondary objectives include documenting the efficacy stratified by minimal inhibitory concentration (MIC) compared with the gentamicin peak level in order to estimate a pharmacodynamic criterion. We will also attempt to determine whether gentamicin monotherapy induces antimicrobial resistance among treatment failures. Lastly, we will evaluate the tolerability of 360 mg of IM gentamicin, stratified by subject weight (i.e. weight based dosing). The specific aims are:

- 1) Determine the proportion of persons whose pharyngeal gonococcal infections are cured with a single dose of 360mg gentamicin intramuscularly alone.
- 2) Evaluate the *renal safety* and tolerability of 360mg IM of gentamicin.
- 3) Document mean peak gentamicin levels following 360mg IM of gentamicin stratified by weight.
- 4) Estimate the best pharmacodynamics criterion (i.e. peak/MIC ratio) for pharyngeal gonorrhea treated with gentamicin using individual and mean peak gentamicin levels and NG isolate MIC.
- 5) Among treatment failures, conduct exploratory analyses comparing pre- and post-treatment MIC for evidence of induced resistance.

Study Design: Prospective cohort

Study Population & Inclusion Criteria:

Persons diagnosed with pharyngeal gonorrhea who are not yet treated

Exclusion criteria:

- Age less than 16 years
- Receipt of antibiotics in ≤ 30 days
- Known allergy to any aminoglycoside
- History of renal disease (including diagnosis of solitary kidney, chronic renal insufficiency, renal cell carcinoma etc),
- Use of concurrent nephrotoxic drugs or muscle relaxants
- History of diabetes
- History of hearing loss or tinnitus
- Concurrent infection with syphilis or chlamydia
- Pregnancy and/or nursing
- Unable to return for a follow-up visit 4-7 days (+/- 1 day).
- Study team's discretion

Intervention: 360mg IM gentamicin x 1

Primary Outcome: Negative gonorrhea culture 4-7 days (+/- 1 day) after treatment

Sample Size: 60 persons

Statistical Analysis Plan:

[figure not shown]

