- 2) Evaluate the renal safety and tolerability of 360mg IM of gentamicin.
- 3) Document mean peak gentamicin levels following 360mg IM of gentamicin stratified by weight.
- 4) Estimate the best pharmacodynamics criterion (i.e. peak/MIC ratio) for pharyngeal gonorrhea treated with gentamicin *using individual* and mean peak gentamicin levels and NG isolate MIC.
- 5) Among treatment failures, *conduct exploratory analyses* comparing pre- and post-treatment MIC for evidence of induced resistance.

Analyses

The primary endpoint is the pharyngeal cure rate – that is, the proportion of subjects who return for TOC who clear their infections as evidenced by a negative culture 4-7 (+/-1) days after treatment. The cure rate will be calculated as the number of cured subjects divided by the total number of subjects who received treatment and returned for follow-up testing in a modified an intention to treat (mITT) analysis. We will also calculate the 95% CI for this proportion.

$$\text{Cure rate} = \frac{\text{number of subjects with negative pharyngeal culture at TOC}}{\text{number of subjects with + throat test at enrollment \& received gentamicin}}$$

Persons who test negative for NG at their enrollment visit (i.e. infection cleared between initial clinical screening test and enrollment) will be excluded from analysis. Treatment failure will be defined as a positive culture 4-7 (+/-1) days after treatment.

For our second objective, we will obtain pre- and post-treatment serum creatinine. An elevation of >40% will be considered significant. We will evaluate subject's tolerability (Obj. 2) using a standardized symptom questionnaire (see Appendix F) conducted at the TOC visit. The symptoms questioned will include, but not be limited to, rash, tinnitus, decreased hearing, nausea, vomiting, diarrhea, headaches, and decreased appetite. There will also be a section for free response.

Our third objective is to document the pharmacokinetics of 360mg of IM gentamicin by weight. We will obtain serum gentamicin levels at 30, 45 and 60minutes post dosing based on previous studies that estimated that IM gentamicin peaks between 30-60 minutes post-dose.

We will stratify the results by time post-dose, as well as by subject weight in kilograms (categorized).

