In order to estimate the ideal PK/PD criterion, we will compare the MIC of cures to treatment failures using a stratified approach (Table 2), and we will correlate this data with individual peak gentamicin level in order to estimate the ideal pharmacodynamic (PD) criterion (Obj. 4). As these results are ratios and may have a skewed distribution, we will log transform them and calculate a geometric mean. We anticipate that the vast majority of isolates will have a gentamicin MIC ≤ 8 $\mu\text{g/mL}$, and that most subjects' peak concentration will be between 16-27 $\mu\text{g/mL}$ giving a ratio of 2-4. Variations in subjects' weight or the gentamicin MICs might alter those predictions. Assuming an 80% cure rate ($n=40$), and a mean ratio of 3, with a standard deviation of 1, we anticipate a 95% CI of the peak/MIC ratio of 2.7 – 3.3, suggesting that our sample size is adequate to calculate this ratio.

For persons who fail treatment we will also compare the pre- and post-treatment gentamicin MIC to estimate whether single dose gentamicin therapy can “induce” resistance (Obj. 5) in an exploratory analysis. We will consider an increase in the MIC by two doubling-dilutions (i.e. from MIC of 2 to 8 $\mu\text{g/mL}$, or 8 to 32 $\mu\text{g/mL}$) to represent induced resistance, and we will calculate the proportion of isolates among those that fail treatment that demonstrate induced resistance following receipt of gentamicin. Should we see a signal for induced resistance, we plan to apply for additional funding to conduct whole genome sequencing to look for genetic determinants of resistance.

Table 2: Proposed Description of Primary Study Findings

GENTAMICIN MIC ($\mu\text{g/mL}$)	Cure (N=XX)	Treatment Failures (N=XX)	Gentamicin Serum Level (Mean, Range)	Peak/MIC Ratio (Mean, Range)
≤ 1				
2				
4				
8				
16				
32				
≥ 64				

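### As analysed, Aim 4 cannot show that peak/MIC is the best criterion, because the ratio is never set against MIC alone or level alone in relation to cure

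*Combined protocol and SAP*

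**What the plan says.** All participants receive the same treatment, described in Aim 1 as a "single dose of 360mg gentamicin intramuscularly alone". The Objectives section gives "Sample Size: 60 persons". Aim 4, stated there and again under Data Analysis, is to "Estimate the best pharmacodynamics criterion (i.e. peak/MIC ratio) for pharyngeal gonorrhea treated with gentamicin"; the Objectives wording continues "using individual and mean peak gentamicin levels and NG isolate MIC".

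The analysis is set out under Data Analysis, Analyses:

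- MIC is compared between cures and failures in Table 2.
- The text then says "we will correlate this data with individual peak gentamicin level in order to estimate the ideal pharmacodynamic (PD) criterion", without naming a method.
- The ratios are log transformed and summarised by a geometric mean.

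For the levels, the same section predicts: "most subjects' peak concentration will be between 16-27" µg/mL. Its prediction for susceptibility is that the "vast majority of isolates will have a gentamicin MIC ≤ 8" µg/mL. It puts the resulting ratios at 2 to 4. Its adequacy argument takes 80% cure, n = 40, "and a mean ratio of 3, with a standard deviation of 1", and arrives at a 95% CI of 2.7 to 3.3 for the ratio.

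Study Procedures provides one blood sample per participant, at 30, 45 or 60 minutes by rotation. Table 2 has one row per MIC value, counts of cures and failures, and then a single level column and a single ratio column (mean and range), neither split by outcome.

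**The concern.** A claim that peak/MIC is the best index needs evidence that both parts matter: that MIC relates to cure, and that at a given MIC a higher level goes with more cures. The plan looks at the first and has no defined analysis of the second. An association between the ratio and cure could therefore come entirely from MIC, or entirely from level, and still be reported as a peak/MIC criterion.

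The mean-peak version makes this plain. If every MIC is divided into the same number, the result is MIC in other units. The data analysis plan for monitoring says the goal is to use gentamicin with a second agent, so readers may take up a reported criterion although serum level was never shown to bear on cure.

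**Working it through.** **1. The plan's own figure.** Inputs from Analyses: mean 3, SD 1, n = 40. The interval is 3 ± 1.96 × 1/√40 = 3 ± 0.31, or 2.69 to 3.31. The stated 2.7 to 3.3 reproduces. (40 is 80% of 50; 80% of 60 is 48, which gives 2.72 to 3.28 and changes nothing here.) The figure describes the precision of a mean ratio. It is not a threshold and compares no indices.

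**2. Mean peak.** Ratio = c/MIC, so log2(ratio) = log2(c) − log2(MIC). The correlation with log MIC is exactly -1. If means by weight stratum are used, this holds within each stratum.

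**3. Individual levels, by MIC row.** The range 16 to 27 spans 27/16 = 1.69-fold, or log2(1.69) = 0.755 of a doubling. Ratios for participants inside that range:

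| MIC (µg/mL) | Ratio |
|---|---|
| 2 | 8 to 13.5 |
| 4 | 4 to 6.75 |
| 8 | 2 to 3.4 |
| 16 | 1 to 1.7 |

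Adjacent rows do not overlap, so between rows the ratio is ordered by MIC. Within a row, all variation in the ratio comes from level.

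**4. How closely the ratio tracks MIC overall.** Assume that level and MIC are independent. Then r = −SD(MIC)/√(SD(MIC)² + SD(level)²), with SDs on the log2 scale. The SD of level depends on how many participants 'most' means:

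- ±2 SD: 0.755/4 = 0.189
- 80%: 0.755/(2 × 1.28) = 0.295
- 68%: 0.755/2 = 0.377

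*(a) Using the plan's ratio SD.* A lognormal with mean 3 and SD 1 has log2 SD = √ln(1 + 1/9)/ln 2 = 0.468. MIC's share of the variance is 1 − SD(level)²/0.468².

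| Reading of 'most' | MIC share | r |
|---|---|---|
| ±2 SD | 84% | -0.92 |
| 80% | 60% | -0.78 |
| 68% | 35% | -0.59 |

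*(b) Assuming an MIC SD instead*, with SD(level) = 0.189. An MIC SD of 0.7 gives r = −0.7/√(0.49 + 0.0356) = -0.97. An MIC SD of 1.0 gives r = -0.98.

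*(c) MICs all at 8.* The ratio is level/8 and carries only level. The plan's expected ratio of 2 to 4 is close to 16/8 to 27/8 = 2 to 3.4, so this case fits its figures.

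**5. What a direct test could show.** At 80% cure, 50 to 60 evaluable participants give 10 to 12 failures. Simulation used 400 runs per scenario, cure generated from the true log2 ratio, an assumed odds ratio of 2 or 4 per doubling, three assumed MIC distributions, and the 95% and 68% readings of 'most'. A likelihood-ratio test for level added to MIC had power of about 7% to 34%. The mean gain in AUC of the ratio over MIC alone was 0.01 to 0.09.

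**The case against.** The strongest reply is that Aim 4 names its index in advance and only means to estimate its value, so no contest between indices was promised. The wording allows this. It does not rescue the analysis, because the plan gives no method for finding a target value, and a mean ratio with its CI is not one.

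A second reply is that MIC alone is examined: the comparison of cures with failures comes first, and Table 2 shows level in its own column within MIC rows. That is correct and should be credited. But the level column mixes cures and failures, so the needed comparison at equal MIC is missing, and the correlation with individual level is undefined.

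Third, a reader might infer that one fixed dose makes the ratio almost a relabelled MIC even with individual levels. The documents do not support that as a general statement. They give no MIC distribution, the rows of a blank Table 2 are not expected data, and the plan's ratio SD is compatible with MIC supplying as little as 35% of the variance. With MICs clustered at 8 the direction reverses.

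A reader might also infer that the criterion will be carried to another dose or regimen. The protocol states a goal of combination use, but says nothing about transferring the criterion.

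**Conclusion.** As analysed, Aim 4 cannot establish peak/MIC as the best criterion. This rests on the design and the planned analysis: one dose, one timed level per participant, no comparison of the ratio with MIC alone or level alone in relation to cure, level pooled over outcomes in Table 2, and an adequacy argument about the precision of a mean. It holds whichever component dominates the ratio.

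Only the mean-peak redundancy is exact, for a single overall mean. For individual levels, r of about -0.59 to -0.92 follows from the plan's ratio SD under independence and a lognormal shape. Values near -0.98 require a wider MIC spread that is assumed. The power range rests on assumed odds ratios and MIC distributions. This is a secondary aim, and the correction is a modest one.

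**What to change.** - Do not present the mean-peak ratio as evidence separate from MIC.
- Fit cure on log2 MIC and log2 individual level as two terms, by penalised or exact logistic regression, adjusted for draw time where feasible. The ratio is the special case of equal and opposite slopes. Show MIC-only and level-only results alongside.
- In Table 2, split level by cure and failure within each MIC row.
- Report estimates with confidence intervals and no significance gate. At 7% to 34% power, a gate would usually discard a true peak/MIC effect.
- State that peak/MIC is pre-specified and not compared with other indices, and label Aim 4 exploratory. At present only the induced-resistance aim has that label.

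The cost is a small set of extra models and one wider table, on data already to be collected. The downside is that with about 10 to 12 failures the level term will be imprecise. A null result would not rule out a level effect, and the claim becomes more modest.
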